7.7.3 Patient characteristics (secondary objective 1)

Summary descriptive statistics will be presented by the four cohorts (section 7.2.2) and *described both at diagnosis and treatment index dates in each cohort*. The following will be described at diagnosis date and also treatment index date: patient demographics and clinical characteristics. Where available, a description of COVID-19 illness onset (time to diagnosis), associated symptoms and time to hospitalization for COVID-19 infection will be presented.

Data will be further stratified by subgroups of special interest (see section 7.2.4).

7.7.4 Estimation of incidence of study adverse events of interest and disease outcomes (secondary objectives 2 and 3)

The crude incidence rate of the individual outcome relevant to each sub-cohort reported during person-time treated for each exposure group will be calculated. The crude person-time from relevant index date will be calculated for the following groups:

- Use of systemic glucocorticoids without other treatments for COVID-19 (drug and respiratory support)
- Use of systemic glucocorticoids plus other treatments for COVID-19 (drug and respiratory support)
- Only other treatments and respiratory support with no steroids
- No specific treatments for COVID-19 infection (other concomitant treatments are allowed are allowed)

Only the earliest eligible treatment is considered, and for patients who switch to another treatment (including switch to another glucocorticoid), their follow-up is censored at date of switching. The number and reasons for patients censoring will be reported.

We will calculate both, the incidence proportion and the incidence rate. The numerator for both (risk and rate) will be comprised of counts of incident events of interest during the person-time as defined above recorded during each cumulative interval and summed to reflect the cumulative count for the interval.

The crude cumulative incidence rate will be calculated according to the formula:

$$\frac{\text{Total number of patients on Rx with first event during cumulative interval of interest}}{\text{Total person-time at risk (days)}} \times 100$$

The crude incidence proportion will be calculated according to the formula:

$$\frac{\text{Total number of patients on Rx with first event during cumulative interval of interest}}{\text{Total population at risk at start of study period}} \times 100$$

For each sub-cohort and type of person-time the numerator for each time frame will contain the number of patients for whom an outcome has been recorded in that time frame since the onset of that type of person-time. The crude incidence rate of each outcome within the relevant sub-cohort will be expressed as number of cases per 1,000 patient-days at risk.

The cumulative incidence rate will be reported at the end of follow-up (30 and 90 days).

The person-time estimation and the calculation of the crude incidence rate for secondary objectives 2 and 3 will be similar except for the outcomes being considered in each case. For secondary objective 2, adverse events of interest for glucocorticoids (listed in Section 7.3.3) will be the outcome, and for secondary objective 3 mortality and other disease outcomes (Section 7.3.4) will be the outcome.

Both stratification and adjustment will be used as a method to deal with confounders.

In order to examine risk factors of the outcomes of interest, data will also be stratified by subgroups of interest (7.2.4) and stratum-specific crude incidence rates will be calculated. The stratification variables include the healthcare setting, glucocorticoid user type (naive, prevalent) treatment groups and subgroups of special interest.

Separate Cox regression models will be used to estimate adjusted cause-specific HR³ (in order to account for competing events) for each outcome **within** the following four treatment groups:

- Use of systemic glucocorticoids without other treatments for COVID-19 (drug and respiratory support)
- Use of systemic glucocorticoids plus other treatments for COVID-19 (drug and respiratory support)
- Only other treatments and respiratory support with no systemic glucocorticoids

³ Cause-specific HR are to be interpreted as instantaneous risk estimates and not as cumulative risk estimates; cumulative risks estimates are subject to competing events <https://pubmed.ncbi.nlm.nih.gov/30012114/>

- No specific treatments for COVID-19 infection (other concomitant treatments for indications other than for COVID-19 are allowed)

In addition to stratified analysis, for each of the above four treatment groups, two sets of Cox regression models will be run:

- 1) A model that is adjusted for a list of predefined confounders
- 2) A model that is adjusted for a high dimension propensity score that is derived through large-scale modelling, using all available covariates in each dataset (Section 7.7.5)

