7.2 Setting

The proposed setting for this study will be within seven European countries (Belgium [general practice EHR], Netherlands [general practice EHR], Germany [general practice EHR], France [general practice EHR], Italy [general practice EHR], Spain [general practice EHR, hospital EHR], and the United Kingdom [general practice EHR]).

The study will be conducted using data from multiple real-world data (RWD) sources previously mapped to the OMOP CDM in collaboration with the OHDSI and European Health Data and Evidence Network (EHDEN) initiatives.

Each cohort is defined in a separate setting (either hospital or primary care) based on the data source type and will be described at diagnosis of diagCOVID-19 or labCOVID-19 accordingly. The follow up will take place in the same setting and switch of setting (hospitalization for ambulatory cohorts or discharge for hospital cohorts) during follow up will be captured as an outcome.

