7.3.2.3 Operationalization of exposure metrics

Cumulative duration

For glucocorticoids used in COVID-19 indication

Exposure to a treatment will commence on the date of the first qualifying record, subject to satisfying all inclusion criteria listed in section 7.2.2. Each drug exposure record has a start date and inferred end date, which is either explicitly entered or derived from other available information, such as days' supply or refills. Duration of each episode will be calculated as end date minus start date or directly from days' supply variable, whatever available. For each patient, the cumulative duration of use will be calculated as the sum of the duration of treatment episodes.

Table 3 Calculation of duration of use and end of treatment across databases

	IPCI	UK IMRD	Germany DA	Belgium LPD	SIDIAP	France LPD
If days_supply is missing	Use amount and dose extracted from the sig	Use daily dosage along with prescribed quantity	Impute with the most frequent daily dosage or DDD at a therapy level	Use calculated quantity/units_per_day.	Use the quantity, daily dosage and DDD of each drug	Use the quantity and daily dosage of each drug
If still missing	Use the DDD and prescribed quantity	Impute most frequent daily dose at the drug level	-	-	-	-
If still missing	Use the modal duration in the database					

DDD= defined daily dose; sig - the directions ('signetur') on the drug prescription as recorded in the original prescription (and printed on the container) or dispensing record from the physician.

Daily dose

For glucocorticoids used in COVID-19 indication, the prescribed daily dose at initiation of glucocorticoid (treatment index date) will be recorded and categorized in low and high dose. The definition of low dose and high dose will use the cut off defined by WHO in their prospective meta-

analysis from REACT subgroup (16), namely: 15 mg/d of dexamethasone, 400 mg/d of hydrocortisone, and 1 mg/kg/d of methylprednisolone.

The current recommendation is to use 10 mg of dexamethasone for maximum 10 days, administered orally or intravenously. In case glucocorticoids other than dexamethasone are administered, their dose will be converted in prednisolone equivalents as described:

<https://emedicine.medscape.com/article/2172042-overview>

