Only the first episode of exposure will be considered, patients being censored when they switch to another treatment (including switch to another glucocorticoid) or when follow up ends. Duration of follow-up for each treatment cohort will be summarized and will constitute the denominator for calculation of effect estimates. A persistence window of 7 days between drug utilization records for each study drug will be allowed considered as continuous exposure for the outcome's assessment.

In case that more than 70% of the patients are censored, a sensitivity approach will be applied for objectives 2 and 3 (see Section 7.7.8).

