7.7.8 Sensitivity analysis

For objective 2 and 3, with regards to the reference group for incidence rates

As a sensitivity analysis, the reference group for incidence rates will be replaced with ‘other immunotherapies’ (see Appendix 3 for details).

For prevalent users’ cohorts, the definition of remote users:

A sensitivity analysis to exclude those patients for whom short term duration of corticosteroid use (14 days) is identified prior to COVID-19 diagnosis.

For objectives 2 and 3, if the number of patients censored due to switching is higher than 70%, a sensitivity analysis will be performed, namely an intention to treat approach (ITT), such that after initial exposure is defined to allocate patients to one of the four treatment groups, the denominator is then person-time observed (irrespective of treatment status), rather than person-time treated.

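### Section 7.7.4: the crude rate formula and its reporting unit differ by a factor of 10, and the crude proportion counts censored patients as event-free over a wrongly dated denominator

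*Protocol*

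**What the plan says.** Section 7.7.4 gives two formulas for secondary objectives 2 and 3, and states that risk and rate share one numerator, counted within the treated person-time: "Total number of patients on Rx with first event during cumulative interval of interest".

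- **Crude rate.** The numerator is divided by days of person-time at risk and multiplied by 100. The text after the formulas gives the unit: "The crude incidence rate of each outcome within the relevant sub-cohort will be expressed as number of cases per 1,000 patient-days at risk".
- **Crude proportion.** The same numerator is divided by "Total population at risk at start of study period" and multiplied by 100.

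Sections 7.3.2.3 and 7.7.4 censor follow-up at a switch to another treatment. Section 7.2.3 adds death, deregistration, end of data collection and the study cut-off.

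An ITT analysis is held in reserve, with its trigger stated in three places. Section 7.7.8 applies it "if the number of patients censored due to switching is higher than 70" percent. Sections 7.3.2.3 and 7.9.1 require only that more than 70% be censored and name no cause.

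**The concern.** Every crude rate for objectives 2 and 3 comes from the first formula. A programmer who follows it and labels the output as the text requires will publish rates ten times too small. If one site corrects this by hand and another does not, the databases will no longer be comparable.

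The proportion matters for a different reason. Its numerator loses patients as they are censored, and its denominator does not. The result is below the 30- or 90-day risk by an amount that depends on how much censoring each group has. The four exposure groups and eight databases need not share the same switching or the same lock date, so figures tabulated side by side can differ for reasons unrelated to risk. Analyses run locally and return only aggregates (section 8.0), and results are not refreshed after extraction (section 7.2.1). A wrong multiplier can be repaired afterwards; a proportion cannot be corrected for censoring from two totals.

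**Working it through.** **1. Scale of the rate.** Illustrative inputs: 12 first events in 8,000 patient-days.

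- Formula as written: 12 / 8,000 × 100 = 0.15, a rate per 100 patient-days.
- Stated unit: 12 / 8,000 × 1,000 = 1.5 per 1,000 patient-days.
- Ratio: 1,000 / 100 = 10, independent of the data.

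The × 100 in the proportion is correct, since it gives a percentage.

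**2. Date of the denominator.** Section 7.2.1 starts the study period on 1 January 2020. Section 7.2.3 starts follow-up at the index date, and section 7.7.4 itself counts person-time from the relevant index date. The denominator wording agrees with neither of the last two.

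**3. Effect of censoring with an index-date denominator.** The protocol gives no event or switching rates, so both are assumed. For the true 30-day risk R, take 26%, the figure that section 5.0 gives as a lower bound for case fatality in UK hospitals; it serves only as a round value. Assume a constant event hazard h and a constant, independent censoring hazard s, with s set so that a share c is censored before day 30.

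- h = −ln(1 − 0.26) / 30 = 0.01004 per day
- c = s / (s + h) × [1 − exp(−30(s + h))], solved for s
- crude proportion = h / (s + h) × [1 − exp(−30(s + h))]

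| Censored by day 30 | s per day | Crude proportion | Shortfall relative to 26% |
|---|---|---|---|
| 30% | 0.01404 | 21.4% | about 18% |
| 50% | 0.02792 | 18.0% | about 31% |
| 70% | 0.05073 | 13.8% | about 47% |

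Other true risks behave alike: 10% reads 8.4%, 7.1% or 5.6%; 5% reads 4.2%, 3.6% or 2.9%; 20% reads 16.6%, 14.0% or 10.9%. The results depend only on R and c at the chosen horizon, so they apply equally at day 90.

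**4. Reach of the ITT analysis.** None of the three triggers is met at 70% censoring or less, so every row above could stand uncorrected. When triggered, section 7.7.8 replaces treated person-time by observed person-time. It does not mention the proportion.

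**5. Lock dates.** Table 1 lists HM Hospitales at April 2020 and UK IMRD at June 2020. Taking the last day of each month and subtracting 90 days gives 31 January 2020 and 1 April 2020. If those locks are final, patients indexed later cannot complete 90 days, and the crude proportion counts them as event-free unless an event was already recorded.

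**The case against.** The unit is stated in plain words, so a careful programmer would probably use 1,000. The intended denominator can also be recovered, because section 7.7.4 refers to the index date and section 7.3.2.3 classifies patients at the treatment index date. The proportion is labelled crude, numbers and reasons for censoring will be reported, heavy censoring is listed as a limitation in section 7.9.1, and a footnote in section 7.7.4 warns about competing events. The sentence naming 30 and 90 days refers to the rate. These points reduce the likely harm, but the written formula remains wrong. Objectives 2 and 3 are framed at 30 and 90 days, and the proportion's numerator is tied to the cumulative interval, so it will be read as a 30- or 90-day risk.

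Four stronger readings are tempting and not supported:

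- *All crude results are biased low.* Once rescaled, the person-time rate is a valid on-treatment measure. The censoring fault concerns the proportion.
- *Glucocorticoid follow-up ends near day 17.* This adds a course length ("for maximum 10 days, administered orally or intravenously") to the gap rule ("A persistence window of 7 days between drug utilization records for each study drug will be allowed"). The first is a reported recommendation for one drug and does not limit recorded exposure. The second bridges gaps between records, and no tail after the last record is stated. Plain discontinuation is not named as a censoring event, although the phrase person-time treated suggests it.
- *The ITT analysis can be triggered only by switching.* That holds for section 7.7.8 alone. The fault is that the three statements disagree.
- *Hospital patients accrue unobservable days after discharge.* Section 7.2.3 does not list discharge, but section 7.2 keeps follow-up in the same setting and says "discharge for hospital cohorts) during follow up will be captured as an outcome". This needs clarifying; inflated person-time is not shown.

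**Conclusion.** The point holds for the rate formula and for the proportion. The factor of 10 is certain and rests on no assumption. The mismatch between numerator and denominator in the proportion is also in the text, and understatement follows whenever censored patients would have had later events within the horizon. Its size is not known: the relative shortfall of roughly 16% to 47% covers true risks of 5% to 26% with 30% to 70% censored, under constant hazards and independent censoring. If switching follows deterioration, the true error could be larger or smaller. The January 2020 date is most likely a wording slip, and correcting it does not remove the censoring problem. The lock-date limits assume that the Table 1 dates stay as listed; they are labelled actual or future and may move.

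**What to change.** - **7.7.4, rate:** change the multiplier from 100 to 1,000.
- **7.7.4, proportion:** define the denominator as patients in the exposure group who are at risk at their own index date. Report 30- and 90-day risk by the Aalen-Johansen cumulative incidence, with death as a competing event for non-fatal outcomes, and keep the on-treatment rate beside it. State that the estimator assumes non-informative censoring.
- **7.3.2.3, 7.7.8 and 7.9.1:** use one ITT trigger, either any censoring or switching only, and say that the ITT analysis covers the proportion as well as the rate.
- **7.2.3:** for clarity, state that observation in HM Hospitales ends at discharge for in-hospital outcomes.
- **Reporting:** give 90-day figures only where the final lock date allows 90 days of follow-up.

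The cost is mainly text, plus a standard estimator that uses dates already extracted. Two losses follow. There may be fewer 90-day results, chiefly for HM Hospitales. In DA Germany, LPD France and LPD Italy, which section 7.9.2 says record no vital status, death cannot enter as a competing event, and the tables should say so.

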7.7.5 High dimension propensity score

The primary confounding adjustment strategy that will be employed is propensity score adjustment through large-scale modelling, using all available demographics, clinical conditions, and drug groupings in the 30 days and 365 days pre-index intervals as baseline covariates. (26,27) The complete list of covariates that will be used to calculate the propensity score are the 'OHDSI covariates' as described in the publication by Tian et al. (2018) (27)

Propensity scores will be calculated using L1-regularisation (i.e. LASSO regression) using all 'OHDSI covariates' (listed in Tian et al., 2018) to predict the treatment exposure of interest by penalizing the loss function to help simplify the model specification and to avoid overfitting. This approach of using L1-regularisation has been shown to achieve more robust treatment prediction and covariate balance when compared to a high-dimensional propensity score model. (27) The PS will be then included in the Cox model as an independent variable, to obtain adjusted the incidence rates.

An added advantage of using propensity scores in a regression model, rather than individual covariate adjustment, is that propensity scores are more robust when dealing with rare outcomes (28)

7.7.6 Explore the performance of different COVID-19 coding definitions (secondary objective 4)

The PheValuator is a tool that can be used to estimate the performance of rule-based coding definitions when validation by clinical adjudication of patient records is not possible. (29) This tool will be used to evaluate different COVID-19 definitions as described in section 7.3.1. The method involves three steps:

- (1) Developing a probabilistic diagnostic predictive model for a rule-based case definition:
- (2) Determine the probability for everyone in a large group of subjects to be a case.
- (3) Evaluating the performance characteristics of the rule-based case definition.

This process can be repeated for each case definition constructed.

To construct the diagnosis predictive model, a very specific outcome cohort is needed (where cases have a high certainty to be true positives) which for this study will be the laboratory confirmed SARS-CoV-2 PCR test cases (cCOVID-19). This outcome cohort is nested in the target cohort which contains all subjects positive and a random selection of all subjects negative from the study population, to be used for the model.

This specific outcome cohort will be used to discriminate between positive and negative cases and to both ‘train’ and test the diagnostic prediction model. The PatientLevelPrediction R package (<https://github.com/OHDSI/PatientLevelPrediction>) will be used to create this model and all available data (except the code used to create the true positives) of a 75% random sample of each target cohort will be used.

Once the model is developed, internally validated on the remaining 25% of each target cohort dataset, calibrated and achieves good performance characteristics, this model will be applied to a larger study cohort (called the evaluation cohort, which is also sampled randomly from the study population), where each subject will have a predicted probability calculated for the case definition of interest. The probability of the case definition determined by the model is then used as the probabilistic gold standard with which to examine the following the performance characteristics of each case definition:

- (1) Sensitivity defined as True Positives/ (True Positives + False Negatives)
- (2) Specificity defined as True Negatives / (True Negatives + False Positives)
- (3) Positive Predictive Value defined as True Positives/ (True Positives + False Positives)
- (4) Negatives Predictive Value defined as True Negatives / (True Negatives + False Negatives)

In addition, the contribution of each patient to each of the five case definitions will be presented in aggregate in a 5 by 5 matrix. This will offer insight in the performance of each definition relative to each other and the potential gains of using a broader vs a narrower definition.

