7.1 Study Design

This is a descriptive cohort study using secondary data sources (electronic medical records) from eight databases in seven European countries reflecting either hospital or ambulatory care setting. The study population will be comprised of a cohort of diagCOVID-19 or labCOVID-19 patients in the database within the study time period.

Patients may be either diagnosed and followed-up in an outpatient or in an inpatient setting (according to the database) and they might be new users or prevalent users of systemic glucocorticoids. Based on these 2 characteristics, four mutually exclusive cohorts will be created overall. Not all cohorts can be constructed in each database. They will be used differently depending the objective as mentioned in the analysis section. An overview of the study design is provided in Figure 1 below.

Patients will be followed during the study period from COVID-19 diagnosis date to assess the utilization of systemic glucocorticoids specifically indicated for the treatment of COVID-19 and from treatment index date for the occurrence of outcomes of interest.

[figure not shown]

Figure 1 Study design

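### Objective 4 trains its reference model on a case-enriched cohort and applies it to a random one with no written prevalence correction, so accuracy estimates are biased if negatives are subsampled

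*Protocol*

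**What the plan says.** Protocol section 7.7.6 sets out the procedure in order.

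- **Target cohort.** PCR-confirmed cases are the outcome. The cohort in which they are nested "contains all subjects positive and a random selection of all subjects negative from the study population".
- **Training.** All available data except the code that defines the positives, "of a 75% random sample of each target cohort will be used".
- **Checking.** The model must be "internally validated on the remaining 25% of each target cohort dataset, calibrated and achieves good performance characteristics". The 25% is tied to internal validation; no dataset or prevalence is named for the calibration.
- **Application.** Next, "this model will be applied to a larger study cohort (called the evaluation cohort, which is also sampled randomly from the study population".
- **Use.** The predicted probability "is then used as the probabilistic gold standard" for sensitivity, specificity, PPV and NPV of each definition.

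The section gives no sampling fraction for negatives, and no weight, intercept offset or recalibration to the prevalence of the evaluation cohort. Section 7.1 describes the frame differently from what a diagnostic model needs: "The study population will be comprised of a cohort of diagCOVID-19 or labCOVID-19 patients in the database". The prevalence in the sampling frame is therefore also open.

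**The concern.** The target cohort is sampled on the outcome and the evaluation cohort is not. A model that is well calibrated where cases are over-represented gives probabilities that are too high where they are not. This matters more here than in ordinary prediction, because discrimination is not the end product. The probabilities themselves are summed to form the true and false positives and negatives. Most evaluation subjects are not flagged by a given definition, so a small excess probability in each of them adds up to many false negatives that do not exist.

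At stake are the absolute accuracy values reported for objective 4 and the comparison of broader with narrower definitions that section 7.7.6 sets out to make. Section 7.9.1 also cites objective 4 as mitigation for misclassified COVID-19 diagnoses.

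**Working it through.** The protocol states no accuracy value, sampling fraction or prevalence for objective 4, so there is no figure to reproduce. The check is algebra, then a hand calculation, then simulation.

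**1. Size of the shift.** Let π be the prevalence, x the predictors and f the fraction of negatives kept.

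- Population odds: π·P(x | case) / [(1 − π)·P(x | non-case)].
- Target-cohort odds: π·P(x | case) / [f·(1 − π)·P(x | non-case)] = population odds / f.

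The logit is too high by −ln(f) for every subject. This holds for any well-calibrated model, not only logistic regression.

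**2. Is f below 1?** With P positives and Q negatives in the study population, the target cohort holds P + fQ subjects. The evaluation cohort comes from the same population, so it has at most P + Q. If the evaluation cohort is larger than the target cohort, as the text most naturally reads, then P + fQ < P + Q and f < 1.

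**3. Hand calculation (limiting case).** Assume prevalence 5%, true sensitivity 0.70, specificity 0.99, and the definition as the only predictor.

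- Flagged share: 0.05 × 0.70 + 0.95 × 0.01 = 0.0445. True PPV = 0.035 / 0.0445 = 0.787, odds 3.684.
- Unflagged share: 0.9555. Case probability = 0.015 / 0.9555 = 0.0157, odds 0.01595.
- There are 0.95 / 0.05 = 19 negatives per positive. Keeping 4 gives f = 4/19 = 0.211 and 1/f = 4.75.
- Flagged odds: 3.684 × 4.75 = 17.5, probability 0.946. Unflagged odds: 0.01595 × 4.75 = 0.0758, probability 0.0704.
- Estimated sensitivity = 0.0445 × 0.946 / (0.0445 × 0.946 + 0.9555 × 0.0704) = 0.0421 / 0.1094 = 0.385. Estimated PPV = 0.946. Estimated NPV = 1 − 0.0704 = 0.930, against a true 0.984.

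**4. With other informative predictors.** These reduce the bias without removing it. The simulation used 400,000 subjects, the same definition, and two further predictors:

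| Negatives per positive | f | 1/f | Hand limit, sensitivity/PPV | Simulated, sensitivity/PPV |
|---|---|---|---|---|
| 10 | 0.526 | 1.9 | 0.581 / 0.875 | 0.63 / 0.82 |
| 4 | 0.211 | 4.75 | 0.385 / 0.946 | 0.51 / 0.86 |
| 1 | 0.053 | 19 | 0.165 / 0.986 | 0.35 / 0.90 |
| all 19 | 1 | 1 | 0.70 / 0.79 | no bias |

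A separate run at 4:1 gave 0.48/0.88. With stronger predictors, sensitivity at 1:1 was 0.51 to 0.62. Adding ln(f) recovered the truth to within 0.01 in the tabulated simulation.

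**5. Would the hold-out reveal it?** This run assumed a prevalence of 2.2%. That is 124,221 / 5.6 million, and it assumes that the largest case count in section 7.5 belongs to SIDIAP, which the protocol does not say. The model was fitted on 75% of an enriched cohort and recalibrated on the other 25%. For f below 1, hold-out calibration looked good (intercept −0.06 to 0.00, slope 0.98 to 1.00). Yet at f = 0.1, in a random evaluation cohort:

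| | Truth | Uncorrected | With ln(f) |
|---|---|---|---|
| Mean probability | 0.022 | 0.092 | 0.021 |
| Sensitivity | 0.59 | 0.22 | 0.60 |
| PPV | 0.56 | 0.89 | 0.56 |
| Specificity | 0.990 | 0.997 | 0.990 |
| NPV | 0.991 | 0.927 | 0.991 |

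**6. Broad against narrow.** The distortion is not the same for every definition. Suppose A flags 1,000 subjects at probability 0.90 (900 expected cases) and B flags 10,000 at 0.05 (500). At f = 0.1, A's odds go from 9 to 90 (probability 0.989, 989 cases). B's go from 0.0526 to 0.526 (probability 0.345, about 3,448 cases). A is truly the more sensitive, but B appears more than three times as sensitive as A. This is constructed to show that reversal is possible, not that it is typical.

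**The case against.** **The missing correction is read from silence.** The word for calibration is attached to no dataset. The section names a published tool and an R package whose procedures are not reproduced, and an SAP may exist. Any of these could supply a prevalence correction. This limits certainty and stands to that extent. It does not remove the mismatch: the protocol fixes outcome-dependent sampling for one cohort and random sampling for the other, and the target cohort is the only dataset named before the model is applied.

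**The size is not known.** This stands. Neither f nor prevalence is given, and section 7.1 taken literally restricts the frame to COVID-19 patients. At a fixed ratio, higher prevalence brings f closer to 1. At 60% prevalence there are only 0.40 / 0.60 = 0.67 negatives per positive, so even 1:1 would need every negative and no bias arises. High prevalence alone is no protection, however: at 30% prevalence and f = 0.1, a broad definition's sensitivity fell from 0.85 to 0.60.

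**A reader might infer that objective 4 can no longer rank definitions.** That is not shown in general. In a simulation of five definitions, conditionally independent given disease, the order by sensitivity and by PPV was unchanged in all 36 scenarios. Reversal needs a particular structure, as in step 6. The 5 by 5 matrix and the effect on cohort size need no model and are unaffected.

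**A reader might infer that the choice of main definition is undermined.** Section 7.3.1 already fixes it as the catch-all and runs all analyses on it.

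**A reader might infer a further bias from overlap.** All positives are in the target cohort, so any PCR positive drawn into the evaluation cohort has already been used to fit or test the model, unless such subjects are excluded. The section does not say, and the effect has not been quantified.

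**Conclusion.** The point holds conditionally. If section 7.7.6 is followed as written and negatives are subsampled, predicted odds are inflated by 1/f. Sensitivity and NPV come out too low, PPV and specificity too high, and the hold-out check cannot detect it.

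At an assumed 5% prevalence and true sensitivity/PPV of about 0.70/0.79, the estimates are roughly 0.6/0.83 at 10:1, 0.5/0.87 at 4:1 and 0.3/0.9 at 1:1. These rest on assumed prevalence, sampling ratio and predictor strength. The direction does not, and the bias is zero at f = 1.

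The documents do not support saying that every reported accuracy value is certain to be wrong. They do support saying that absolute values, and comparisons of broader with narrower definitions, would be unreliable without a correction. The consequence stays within a secondary, exploratory objective: the main definition and the primary, safety and mortality analyses do not use these probabilities. The change is worth making because it costs almost nothing.

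**What to change.** Amend section 7.7.6 to:

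1. Record f, the fraction of negatives taken into the target cohort, for each database where the model is built.
2. Either give the target cohort the population prevalence (positives and negatives sampled at the same rate), or add ln(f) to the linear predictor before computing probabilities in the evaluation cohort. Weighting sampled negatives by 1/f in fitting and calibration is equivalent.
3. State the data on which calibration is judged, and check it in a random, non-enriched sample. This is feasible only where PCR results exist, which section 7.9.1 says is currently SIDIAP alone. Use it to verify the offset, not to force the sum of probabilities to equal recorded PCR positives, because untested true cases sit among the negatives.
4. As an optional safeguard, give subjects who are in both cohorts cross-fitted predictions.

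The sampling frame should be stated at the same time, given the wording of section 7.1, but the correction is needed whichever frame is chosen. The cost is a few sentences and very little code for items 1 and 2, and one extra calibration check in one database. No new data are needed.
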